6.3 Schedule of Procedures and Assessments

The study-specific assessments are detailed in this section. All on-site visit procedures are allowed a window of \pm 10 days unless otherwise noted.

A written, signed, informed consent form (ICF) and a Health Insurance Portability and Accountability Act (HIPAA) authorization must be obtained before any study-specific assessments are initiated. A copy of the signed ICF will be given to the subject and a copy will be filed in the medical record. The original will be kept on file with the study records.

Pre-operative period

The pre-operative period will be defined as the time between a new patient visit to plastic surgery up to and including the day of surgery. After informed consent has been obtained and during this period of time, patients will be screened for participation in the study via review of their medical record.

Day of surgery

On the day of surgery, patients will undergo a condition-specific physical exam, have vital signs taken, and have their medical history reviewed.

Screening period

The screening period encompasses the pre-operative period up until the day of surgery. The allowable screening window is 6 months prior to the date of surgery. Patients who do not have surgery scheduled within 6 months of screening will be re-screened for eligibility within the screening window.

Intraoperatively at time of bilateral mastectomy

Tranexamic Acid is available as a sterile, single-dose 1g vial that needs to be reconstituted in 1ml of saline, to thus be 1000mg/ml. This 1g vial is readily available in the anesthesia cart in the operating room. Preoperatively, the surgery team will mix this into 40ml of 0.9% Normal Saline to thus produce a 25mg/ml TXA solution. 20ml of this will be passed onto the sterile surgical field for application to one breast pocket at the end of the case prior to closure. 20ml of 0.9% normal saline will also be passed onto the sterile surgical field for use on the control side.

The surgeon will mix the TXA solution and pass onto the surgical field as outlined above. After the completion of the bilateral mastectomy, the plastic surgeon will perform their portion of the procedure. After obtaining hemostasis and irrigating as per standard practice, they shall not use any other hemostatic agents. Immediately prior to final closure, 20ml of 25mg/ml TXA solution shall be infiltrated into the right breast pocket. 20ml of 0.9% normal saline shall be infiltrated into the left pocket. The sidedness of the TXA administration will be documented by the surgery team in our record but kept confidential from the surgery clinic staff to prevent bias at post-operative assessments. The solutions will be allowed to dwell, and JP drains will be kept off bulb suction until the end of the case. Post-procedure, each patient will be provided with standard post-operative instructions which will include a chart to record drain outputs daily for the right and left sides.

Post-Operative Clinic Visits

Drain output will be assessed at each clinic visit to determine timing for removal. Drains will be removed per standard practice at our institution which is when they have produced < 30cc/day for at least 3 days.

At each clinic visits up to one year after surgery, we will assess for clinical signs of hematoma, seroma, and ecchymoses. The number of post-operative clinic visits and their timings will vary by patient. Patients will be managed for hematoma and seroma as per standard procedure, whether with ultrasound, clinic aspiration, IR drain placement, or return to the operating room as deemed necessary by the senior surgeon.

Optional Segments

If patients have multiple visits within each block of the assessment period (1-4 weeks, 5-11 weeks, and 12 week – 1 year), study-specific assessments and procedures may be performed.

7 Reporting and Documentation of Results

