2.3 Secondary Objective(s) and Endpoint(s)

[figure not shown]
Secondary Objective	Endpoint(s)	Time Frame
1. To evaluate the impact of TXA on patient and provider rating of bruising, comparing the TXA side to the control side	
Ecchymosis will be compared between the right and left side at each post operative visit and documented. The observer will be blinded to the laterality of TXA	From application in the operating room to 30 days of follow up
2. To evaluate the impact of TXA on total drain output in the first post operative day	
Total drain output over the life of the drain, compared between control and study groups	From drain placement in the operating room to discharge on POD1
3. To evaluate the impact of TXA on total drain duration	
Total drain duration compared between control and study groups	From drain placement in the operating room to removal of the drain

3 Study Design

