3.1 Characteristics

We propose a prospective, placebo-control trial looking at the effect of topical tranexamic acid on post-operative bleeding, hematoma, seroma, drain output, and bruising in post-mastectomy breast reconstruction. We will recruit patients undergoing bilateral mastectomy at our institution. Patients will be excluded if they have previous history of bleeding or coagulation disorders. Each patient will serve as their own internal control, with one side receiving saline and the other TXA. During surgery and prior to wound closure, we will moisten the wound surface of one side with 20 cc of dilute TXA 25mg/ml solution, and the contralateral with 20cc of saline. Demographics, cancer details, and surgical characteristics will be collected. Outcomes will we assess include hematoma, seroma, reoperation, drain duration, and degree of ecchymosis will be recorded post-operatively for analysis over a 3-month period. The primary outcome will

be presence of hematoma. Secondary outcomes will include seroma, drain output and duration, ecchymosis, and return to operating room.

The surgeon will mix the TXA solution and pass onto the surgical field (detailed in a later section). After completion of the bilateral mastectomy, the plastic surgeon will perform their portion of the procedure. Immediately prior to final closure, 20ml of 25mg/ml TXA solution will be infiltrated into one breast pocket. 20ml of 0.9% normal saline will be infiltrated into the other breast pocket. No other hemostatic agents will be used. The sidedness of the TXA administration will be documented by the surgery team in our record but kept confidential from the surgery clinic staff to prevent bias at post-operative assessments. The solutions will be allowed to dwell while performing incisional closure, and the solutions will be evacuated by the Jackson-Pratt drain when placed to bulb suction at the end of the case. Post-procedure, each patient will be provided with standard post-operative instructions. They will be followed post-operatively for up to 1 year.

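### The team obtaining hemostasis can know beforehand which breast will receive TXA, because section 6.3 fixes the side and nothing conceals it from the operating team

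*Combined protocol and SAP*

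**What the plan says.** **Preparation.** Section 3.1 says "The surgeon will mix the TXA solution and pass onto the surgical field (detailed in a later section"). Section 6.3 repeats this ("The surgeon will mix the TXA solution and pass onto the surgical field as outlined above") and places the mixing before the operation: "Preoperatively, the surgery team will mix this into 40ml of 0.9% Normal Saline to thus produce a 25mg/ml TXA solution".

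**Order of steps and side.** In section 6.3 the plastic surgeon first secures hemostasis: "After obtaining hemostasis and irrigating as per standard practice, they shall not use any other hemostatic agents". Instillation follows, immediately before closure, and the side is printed: "20ml of 25mg/ml TXA solution shall be infiltrated into the right breast pocket", with saline on the left. Sections 3.1, 5.1 and 6.3 (mixing paragraph) refer only to one pocket and the other. The study calendar in 6.1, as it reads in the text available, marks exposure in the left-breast row, although the table layout may have been disturbed in conversion.

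**Masking.** The surgery team records the side, and the record is "kept confidential from the surgery clinic staff to prevent bias at post-operative assessments" (3.1, repeated in 6.3). For ecchymosis, section 2.3 adds "The observer will be blinded to the laterality of TXA". No masking is described for the operating surgeons, the senior surgeon or the patient.

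**Intervention.** Section 6.3 allows ultrasound, aspiration, a radiology drain, "or return to the operating room as deemed necessary by the senior surgeon".

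**Outcomes.** The primary endpoint is presence of hematoma within 30 days (2.2, 3.1). The hypothesis in 2.1 concerns hematoma or seroma that needs intervention. Return to the operating room is secondary (3.1).

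**The concern.** How carefully each pocket is dried before closure is itself a cause of hematoma. If the surgeon knows which side will get the active drug, care may differ between sides without anyone intending it. Extra care on the saline side would hide a real effect. Less care there would create or inflate one. The within-patient design removes confounding by patient factors, but it gives no protection here: both breasts are in the same hands in one operation, so knowledge of the side acts directly on the contrast being tested. Masking clinic staff afterwards cannot undo a difference made in the operating room.

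After surgery, a decision to image, drain or reoperate made by someone who knows the side could also differ between sides. For outcomes defined by intervention, that decision is the outcome.

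**Working it through.** **Step 1. Who can know the side, and when.**

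| Stage | Person | Is the side available? | Masking stated? |
|---|---|---|---|
| Before surgery (6.3) | Surgery team prepares TXA | Yes, the side is printed in 6.3 | No |
| Hemostasis (6.3) | Plastic surgeon | Yes, same reason | No |
| Instillation (6.3) | Operating team | Yes | No |
| Hospital stay (2.3 places discharge on POD1) | Not specified | The surgery team holds the record | No |
| Clinic visits (3.1, 6.3) | Clinic staff | Record kept from them | Yes |
| Bruising rating (2.3, 7.1) | Provider; patient | Not stated for the patient | Observer yes; patient not described |
| Decision to intervene (6.3) | Senior surgeon | Not stated | No |

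The printed right/left rule makes the side knowable before hemostasis. Mixing a solution shows only that TXA will be used, not where. Surgeon preparation matters because, even with a random side, whoever mixes and places the drug can identify the TXA syringe unless the syringes are identical and coded.

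**Step 2. The plan's own figure.** Section 3.2 gives 150 per group for 5% v 0%, alpha 0.05, power 0.80. Taking alpha as two-sided, the unpooled formula is n = (1.960 + 0.842)² × [0.05 × 0.95 + 0] / 0.05² = 7.849 × 0.0475 / 0.0025 = 149.1, rounded up to 150. The stated figure is reproduced.

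**Step 3. Expected events.** Section 1.1 gives 2-5%. On the saline side, 150 × 0.02 = 3 and 150 × 0.05 = 7.5.

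**Step 4. How much one event matters.** Section 7.1 plans chi-squared on breasts. With 150 per arm, a saline-side events, c TXA-side events and m = a + c, the uncorrected statistic is X² = 300(a − c)² / [m(300 − m)].

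- 8 v 1: 300 × 49 / (9 × 291) = 5.61, p = 0.018.
- 8 v 2: 300 × 36 / (10 × 290) = 3.72, p = 0.054.

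The change also holds under an exact paired test with all events discordant: 2 × (1 + 9)/2⁹ = 0.039 and 2 × (1 + 10 + 45)/2¹⁰ = 0.109.

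**Step 5. Illustration with assumed bias.** The documents give no bias size, so these are assumptions: no true TXA effect, independent breasts, the uncorrected chi-squared test, and knowledge of the side lowering the TXA-side event rate by the stated fraction. The entries are the probability of a significant result favoring TXA.

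| True rate | No bias | 20% fewer | 40% fewer | 50% fewer |
|---|---|---|---|---|
| 5% | 2.4% | 5.9% | 13.3% | 19.4% |
| 2% | 2.3% | 3.9% | 6.8% | 9.0% |

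A bias in the other direction would instead reduce the chance of detecting a real benefit.

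**The case against.** The case for the plan has real substance.

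- **Mixing.** A reader might infer that mixing the TXA reveals the side, or that the problem remains however the side is chosen. The documents do not support this for the hemostasis step. If the side were allocated per patient and disclosed only after hemostasis, a surgeon could mix the drug and still not know its destination. The text also separates the surgeon who mixes from the plastic surgeon who obtains hemostasis, and these may be different people. The supportable statement is that the team can know.
- **Detection bias on the primary endpoint.** A reader might infer that the senior surgeon's decisions determine the primary result. They do not define it. The endpoint is presence of hematoma, recorded from examination at clinic visits (6.3, 7.1), where staff are masked. The documents do not say that the senior surgeon operated or knows the side; they only fail to say that this person is masked. What stands is possible detection bias in the intervention wording of 2.1, in return to the operating room, and in hematomas managed before the first clinic visit.
- **Safeguards.** Hemostasis follows standard practice and other hemostatic agents are barred on both sides. This limits differential care but leaves ordinary effort to judgment.
- **Size.** The p-values show that few events make any result fragile, whatever the cause. They do not measure bias. Nor is every one-event change decisive: 6 v 0 and 5 v 0 give p = 0.013 and 0.024 under uncorrected chi-squared. They straddle 0.05 only with a continuity correction (0.039 and 0.071) or an exact paired test (0.031 and 0.063), and the plan specifies neither.
- **No commitment broken.** The plan promises a placebo control and masked assessment, not masked surgeons. This is true, and it is one reason the point is not ranked higher.

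**Conclusion.** The concern holds in a limited form. With the side printed in 6.3 and no concealment from the operating team, those obtaining hemostasis can know the TXA side beforehand, so the primary hematoma comparison is open to performance bias. Neither its size nor its direction can be derived from the documents, and the planned analysis could not recover them. Detection bias is a possibility for the outcomes listed above, resting on an absence of stated masking and not on a statement that the senior surgeon is unmasked.

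The small event count is why it matters: 3 to 7.5 expected saline-side hematomas, assuming the cited 2-5% rate applies and all 150 patients are evaluable. One event can then decide significance. This is a cheap improvement that should be made. It is linked to the side-allocation problem and cannot be solved apart from it.

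**What to change.** Amend sections 3.1 and 6.3 as follows.

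1. Replace the fixed right/left sentences with a side allocated at random for each patient and concealed from the operating team. Reconcile the exposure rows of the study calendar (6.1) with the new text. Without this step, syringes labelled by side would mask nobody who has read 6.3.
2. Have an unscrubbed member of the existing operating-room team prepare two identical 20 ml syringes, one TXA and one saline, labelled only by side. Release them to the field after hemostasis is declared complete on both sides.
3. Hold the key in the encrypted record already planned in 7.1, out of reach of the operating and clinic teams, with a defined unmasking route for safety.
4. Extend the masking sentence to the operating surgeons, the senior surgeon who decides on intervention, and the patient who rates bruising.

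The cost is a protocol amendment, a short work instruction, and syringe preparation outside the scrubbed team. That no extra staff are needed is an assumption; the documents do not describe room staffing. No visits or procedures are added for patients.

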1.1 Background on Indication

Post-mastectomy breast reconstruction has significant physical, mental and emotional benefits for breast cancer patients[1]. However hematoma, seroma and bruising are common complications given the highly vascularized nature of breast tissue[2]. These events can compromise the reconstruction, as well as potentially delay cancer treatments including chemotherapy and radiation by predisposing the patient to infection and wound complications. The hematoma and subsequent reoperation rate in breast surgery has been cited from 2-5% [2], thus topical hemostatic agents are often used intraoperatively. However, these agents are usually expensive, come in varying forms, and difficult to regulate. Prior studies in orthopedics, plastic surgery, and trauma have shown a significant reduction in bleeding, ecchymosis, and need for transfusions with use of Tranexamic Acid (TXA)[3-12]. TXA is a synthetic amino acid that blocks plasminogen conversion to plasmin, to prevent fibrinolysis and stabilize clot formation. Improvement in bleeding and bruising has been described utilizing both intravenous and topical off-label applications of TXA[6, 12]. In breast surgery there have been mixed results to preliminary retrospective studies of both intravenous and topical tranexamic acid, with some decreases in hematoma and seroma rates, and drain volumes[13-15]. The proposed prospective trial will evaluate the efficacy of topical TXA in decreasing hematoma and seroma rates, drain output, drain duration, and ecchymosis in bilateral post-mastectomy breast reconstruction patients. Every patient will serve as their own control. This novel use of TXA in breast surgery may provide a simple, cost-effective, and safe way to improve outcomes in breast reconstruction patients.

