1.2 Background on the Investigational Product(s) and Associated Known Toxicities

TXA is a synthetic amino acid that blocks plasminogen conversion to plasmin to stabilize clot formation [16]. Despite the fact that TXA is only FDA-approved for hemophilia patients to reduce hemorrhage and need for replacement therapy following tooth extraction [16], many high powered double-blind randomized trials have published their results using TXA in other surgical specialties. Prior orthopedic arthroplasty studies have shown that a single intraoperative dose of TXA prior to incision significantly decreases blood loss and transfusion requirements without associated thrombotic complications [6, 7, 11, 17]. These have shown that not only intravenous, but also directly infiltrating the joint topically can decrease bleeding [6, 12]. Furthermore, there have not been any report of increased systemic thrombosis when used topically. In plastic surgery, TXA is routinely dosed intravenously prior to incision for pediatric craniosynostosis cases to minimize blood loss, decrease transfusion requirements, and shorten length of hospital stay [3, 4, 9]. The literature also shows when used topically it can significantly decrease bruising and bleeding in rhinoplasty, rhytidectomy, and liposuction [8, 10, 18, 19].

More recently, there have been retrospective studies in breast plastic and oncologic surgery evaluating the use of TXA without any evidence of thrombotic complications. Weissler et al published a retrospective review of immediate post-mastectomy tissue

expander placement which showed a statistically significant decrease in hematoma with intravenous TXA administration[13]. Perhaps most pertinent for our study is the small trial from Ausen et al in the Netherlands in which they examined topical moistening of mastectomy flaps with a dilute TXA solution. They found no complications were related to topical administration of TXA relative to the control group[15]. This small study trended toward decreasing hematoma rates and drain volumes, and inspired our own study design of using each patient as their own internal control. We hope to build off this study given our large volume of mastectomies, and low risk profile of utilizing topical TXA. Additionally, designing the study such that each patient receives a control and experimental dose (saline on one side, TXA on the other) will help us to control for any confounding patient factors and further validate our results.

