5.1 Dosage and Administration

Treatment will be administered in the operating room at the time of surgery. 20ml of 25mg/ml solution of TXA will be infiltrated into one of the breast pockets and allowed to dwell in the pocket prior to closure. The other side will receive 20ml of plain 0.9% Saline. This will be the only administration of TXA for the duration of the study.

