7.1 Statistical analysis

We will compile an encrypted record of each patient and the study or control solution that was administered to each breast intraoperatively. We will then record data from the condition-specific physical examination at each post-operative clinic visit to track presence of hematoma, presence of seroma, laterality with worse bruising, amount of drain output prior to removal, and number of days with drain prior to removal.

Demographic and surgical details will be collected for each patient. These will include patient demographics (i.e., age, BMI, race, ethnicity), clinical cancer characteristics (i.e., type of cancer, neoadjuvant chemo or radiation, adjuvant chemo or radiation), and post-operative outcomes (i.e., hematoma, seroma, infection, return to the operating room, radiology aspiration or drain placement, clinic aspiration). Results will be analyzed comparing the outcomes of the TXA treated breasts with the Control (Saline) treated breasts using T test for continuous variables, and Chi Squared for categorical variables.

Multivariate regression analysis will also be utilized to assess for the importance of various clinical and demographic factors (BMI, cancer laterality, etc.) on overall outcomes. For ecchymosis, the prevalence of worse ecchymosis with or without TXA will be reported as rated by the provider and patient at post operative visits.

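### The side that receives TXA is never randomised, and Section 6.3 fixes it to the right breast, so the drug effect cannot be separated from a right-left difference

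*Combined protocol and SAP*

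**What the plan says.** The design is within-patient: one breast receives TXA and the other saline. The sections differ on which breast.

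- Section 6.3 (intraoperative procedures) names the side: "20ml of 25mg/ml TXA solution shall be infiltrated into the right breast pocket". Saline goes to the left.
- Section 3.1, in an otherwise matching sentence, says only "20ml of 25mg/ml TXA solution will be infiltrated into one breast pocket".
- Section 5.1 is equally open: "20ml of 25mg/ml solution of TXA will be infiltrated into one of the breast pockets".
- Section 6.1 (study calendar), as it reads in the extracted text, has its only TXA exposure mark on the left-breast row. This may be a merged table cell and should be checked against the original; nothing below depends on it.
- Section 7.1 keeps an encrypted record of "the study or control solution that was administered to each breast intraoperatively". This suggests the side may have been meant to vary, but a record is not an allocation rule.

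Randomisation is mentioned only in connection with other studies, in the background and references. Sections 2.3, 3.1 and 6.3 promise that post-operative assessors will not know the treated side. Section 1.2 justifies the design on the ground that it "will help us to control for any confounding patient factors". The analysis in 7.1 is a t test or chi-squared test of TXA against saline breasts, plus a regression that names BMI and cancer laterality but not breast side.

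**The concern.** Using each patient as her own control removes differences between patients. It does not remove differences between a patient's two breasts; only random allocation of side does that. There are two ways to read the plan, and each leaves a problem.

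**Section 6.3 governs.** Every TXA breast is a right breast and every saline breast a left one. Measured breast-level factors that vary in side between patients, such as cancer side, can be adjusted for. A systematic laterality effect, for example from the operator's position or the order of operating, cannot. It goes straight into the estimated drug effect and can create or hide a benefit.

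**The side is left open.** Sections 3.1 and 6.3 place instillation immediately before final closure, and 3.1 and 6.3 have the surgeon mix the TXA. An unmasked operator could then choose the side after inspecting both pockets, and nothing in the plan prevents it.

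A side printed in the protocol also lets any assessor who knows the protocol infer the treated breast. The bruising outcome in 7.1, "laterality with worse bruising", is the most exposed, because it is a direct and subjective comparison of the two sides.

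**Working it through.** **1. The plan's own figure.** Section 3.2: 5% v 0% hematoma, alpha 0.05 (taken as two-sided), power 0.80, at least 150 per group.

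- Pooled variance: n = [1.960·√(2·0.025·0.975) + 0.842·√(0.05·0.95)]² / 0.05² = 151.9, so 152.
- Unpooled variance: n = (1.960 + 0.842)²·(0.05·0.95) / 0.05² = 149.1, so 150.

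The 150 reproduces. The problem is not the sample-size arithmetic.

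**2. Identifiability (no assumed rates needed).** Write the risk in a breast as patient level + τ·TXA + δ·right. The TXA-minus-saline contrast within a patient is τ + δ if the right breast is treated and τ − δ if the left is.

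- TXA always right: the mean contrast is τ + δ. The TXA and right-side indicators correlate 1.0, and the design matrix (intercept, TXA, right) has rank 2 of 3, whatever the N.
- Side randomised 1:1: the mean contrast is ½(τ + δ) + ½(τ − δ) = τ. The rank is 3 of 3, and both effects can be estimated.

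**3. False-positive rate with no drug effect.** 150 breasts per side, uncorrected chi-squared, two-sided 0.05, sides independent within patient. Fixed-side figures are exact sums over two binomials; randomised-side figures come from 1,000,000 simulated trials. All side rates are assumptions.

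| Side rates | Fixed side | Fixed, continuity-corrected | Randomised side |
|---|---|---|---|
| 5% v 5% | 4.8% | 2.4% | – |
| 4.75% v 5.25% | 5.3% | 2.7% | – |
| 4.5% v 5.5% | 6.6% | 3.5% | – |
| 4% v 6% | 12.0% | 7.2% | 4.9% |
| 2% v 5% | 27.9% | 18.1% | 4.6% |
| 3% v 7% | 35.3% | 25.5% | 4.9% |

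A paired test does not rescue the fixed side. At 2% v 5%, the exact McNemar test (40,000 simulated trials) rejects in 19.1% with a fixed side and 2.1% with a randomised one.

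**4. More patients.** With a fixed side and 4% v 6%, rejection rises from 12.0% at 150 per side to 20.2% at 300 and 35.6% at 600. Recruiting beyond the minimum, as 3.2 intends, makes this worse.

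**5. Hiding a benefit.** Suppose TXA lowers hematoma from 5% to 1%. With no side difference, power is 53.6%. If the always-treated right side carries 2 extra points, the comparison is 3% v 5% and power falls to 13.5%. With the side randomised and the same 2 extra points on the right, power is 42.4%.

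**The case against.** The strongest reply is that no document reports any right-left difference in hematoma, so the bias may be small. That is fair as to size. The table shows that gaps of one point or less leave the error rate at 6.6% or below. The 2–5% range in Section 1.1 is a literature range for breast surgery overall, not a right-left contrast, so the 2% v 5% row has no support from it. The uncorrected test and independent sides are also the less favourable settings for the plan. If 30% of patients with a hematoma on the lower-rate side also had one on the other, 4% v 6% would give about 9% rather than 12%; at 50%, about 7%. None of this touches step 2: a fixed-side trial cannot show that its own laterality effect is small.

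It can also be said that one pocket is less specific than the right pocket rather than contradictory, and that the mandatory wording of 6.3 excludes operator choice. If so, the operator-choice problem goes and the confounding is certain. Either way the sections need one rule. Operator selection and inference of the side by clinic staff are possibilities the plan leaves open, not events it describes.

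Two practical objections stand. Patients already treated on a fixed side would not count towards 150 randomised patients. And covariates are weakly supported for hematoma: at 5%, 300 breasts yield about 300 × 0.05 = 15 events.

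**Conclusion.** The concern holds and must be fixed. With the side fixed as in 6.3, the primary hematoma contrast equals the drug effect plus any right-left difference. The planned analysis cannot separate them at any sample size, and data collected this way cannot be repaired later. That conclusion rests on the text and the algebra alone.

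The size rests on assumed side rates. With no drug effect, the false-positive rate runs from 5.3% for a half-point gap to 12% for 4% v 6% and 35% for 3% v 7%, against about 5% when the side is randomised. Two extra points of risk on the treated side could cut power from 54% to 14%. These figures assume an uncorrected chi-squared test and independence between a patient's breasts; correction or within-patient correlation lowers the false-positive figures.

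The risk to assessor blinding follows from printing the side in the protocol, and depends on whether assessors know that text.

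**What to change.** Reconcile Sections 3.1, 5.1, 6.1 and 6.3 to a single rule: the TXA side is allocated at random, 1:1 right or left, for each patient from a concealed list. Open the allocation in the operating room once hemostasis is complete on both sides, and keep the list from outcome assessors. Remove the fixed right/left wording from 6.3, and correct the calendar row if the original table marks one side.

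Secondary steps:

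- Report any patients already treated on a fixed side separately. The documents do not give accrual status.
- Include breast side and cancer side in the 7.1 regression where event numbers allow. Once the side is randomised, validity does not depend on this.
- Optionally, stratify by cancer side, or mask the surgeon with matched syringes. Masking would need an unblinding route for the washout described in 7.2.

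The cost is one protocol amendment, one randomisation list and one extra operating-room step. Section 6.3 already has both solutions passed to the field, so product handling and visits need not change. The target stays at 150 patients, counted as randomised patients; any treated earlier on a fixed side would have to be replaced to reach it.
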